Immunogenicity		P	P	P		P		P				X	X	-
LY3872386, total antibody, and LY3558533 (free payload) concentration (PK)		P, EOI, 1 hr, and 3 hr	P and EOI	P and EOI	P and EOI	P and EOI	P and EOI	P, EOI, 1 hr, and 3 hr	X	X	X	X	X	
CCI		P and 3 hr	Р	Р	P	P	P	P		X	X	X	X	
		P	P	P	P	P	P	P				X	X	
		P		P		P		P					X	

]	Part B: I	LY38723	86 CCI		Do	osing Sch	edule				
Procedures/ Assessments	Screening			Trea	tment Po	eriod				Follo	w-up		ED	Comments
Visit Number	V1	V2	V3	V4	V5	V6	V7	V8	V	V	V	V		
									801	802	803	804		
Study Day(s)	CC													
		P	P	P		P		P		X	X	X	X	
		P	X	X	X	X	X	X		X	X	X	X	しし し
		Х						X					X	
		P		P				X					X	
		P		P			P			X		X	X	
		P	P	P	P	P	P	P		X	X	X	X	
Ocular pressure, visua acuity, and cataract evaluation	X			X		X			X			X	Х	

Abbreviations: AE = adverse event; AD = atopic dermatitis; CC | d = day(s); DLQI = Dermatology Life Quality Index; EASI = Eczema Area and Severity Index; ECG = electrocardiogram; ED = early discontinuation; EOI = end of IV infusion or subcutaneous dose administration; FSH = follicle-stimulating hormone; I/E = inclusion/exclusion; IL-13 = interleukin 13; IP = investigational product; IWRS = Interactive Web Response System; MDC = Macrophage-derived chemokine; P = predose before IP administration; P1NP = Procollagen 1; PK = pharmacokinetic; POEM = Patient-Oriented Eczema Measure; SCORAD = SCORing Atopic Dermatitis; TARC = Thymus- and activation-regulated chemokine; TB = tuberculosis; TST = tuberculin skin test; V = visit; vIGA-AD = Validated Investigator's Global Assessment for Atopic Dermatitis.

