7.3. Lost to Follow-up

A participant will be considered lost to follow-up if he or she repeatedly fails to return for scheduled visits and is unable to be contacted by the study site. Site personnel or designee are expected to make diligent attempts to contact participants who fail to return for a scheduled visit or were otherwise unable to be followed up by the site.

Site personnel, or an independent third party, will attempt to collect the vital status of the participant within legal and ethical boundaries for all participants randomized, including those who did not get the investigational product. Public sources may be searched for vital status information. If vital status is determined to be deceased, this will be documented, and the participant will not be considered lost to follow-up. Sponsor personnel will not be involved in any attempts to collect vital status information.

8. Study Assessments and Procedures

Study procedures and their timing are summarized in the SoA (Section 1.3).

- Immediate safety concerns should be discussed with the sponsor immediately upon occurrence or awareness to determine if the participant should continue or discontinue study intervention.
- Adherence to the study design requirements, including those specified in the SoA, is essential and required for study conduct.
- All screening evaluations must be completed and reviewed to confirm that potential participants meet all eligibility criteria. The investigator will maintain a screening log to record details of all participants screened and to confirm eligibility or record reasons for screening failure, as applicable.
- Section 1.3 lists the SoA, detailing the study procedures and their timing (including tolerance limits for timing). The specifications in this protocol for the timings of safety and sample collection are given as targets to be achieved within reasonable limits. Modifications may be made to the time points based on emerging clinical information. The scheduled time points may be subject to minor alterations. However, the actual time must be correctly recorded in the CRF.
- Appendix 2 (Section 10.2) lists the laboratory tests that will be performed for this study.
- Appendix 2 (Section 10.2.1) provides a summary of the maximum number and volume of invasive samples, for all sampling, during the study.

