8.4. Pharmacokinetics

For Parts A, B, and C, a maximum of 3 additional blood samples may be collected as additional unscheduled time points during the study, if warranted and agreed upon between both the investigator and sponsor. Refer to Section 10.2.1 for details. Instructions for the collection and handling of blood samples will be provided by the sponsor. Times are referenced at the start of dosing. The actual date and time (24-hour clock time) of each sampling will be recorded. Samples are requested to be taken at the specified time. However, aberrations from the specified sampling times will not be considered protocol deviations as long as the samples are taken, and the actual sampling time is recorded. It is essential that the actual times of doses and samples are recorded accurately on the appropriate forms.

Drug concentration information that may unblind the study will not be reported to CRU or blinded personnel until the study has been unblinded.

In the event of the early discontinuation of a participant in any part of the study, a PK sample will be taken at the early discontinuation visit as an unscheduled sample. The actual date and time of the collection must be recorded.

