9.4.1. Interim Access to Data During the Study

The Lilly sponsor team is not blinded, while the investigator will remain blinded during these reviews. Interim access to safety and tolerability data is scheduled to occur after every dosing session. The purpose of these reviews is to guide dose selection for future dosing sessions and/or inform the design of subsequent studies.

Access to PK data will also occur on a rolling basis during dose escalation as it becomes available. However, IADs are planned to evaluate exposure and available RO data. A review of these data will help guide implementation of this study (such as adjustment to blood sampling time) and support subsequent studies.

[figure not shown]
Four IADs to facilitate AD cohorts and progression to Phase II trial are planned. IADs are planned at the following time points:

- First IAD: 30 days post dose from Part A SAD Cohorts 4 and 5
 - o dose justification for Part B MAD Cohort 1, Period 1
- Second IAD: 30 days post dose from Part A SAD Cohorts 6 and 7
 - o dose justification for Part B MAD Cohort 2, Period 1
- Third IAD: end of Part A SAD cohorts and 30 days post dosing of half of the participants from Part B MAD Cohort 1, Period 1
 - o dose justification for Part B MAD Cohort 1, Period 2, and
- Fourth IAD: End of Part C.

Since PK and RO data will be evaluated on a rolling basis as data become available, review of these data is not limited to the IADs mentioned earlier. These periodic reviews of PK and RO data are not considered as formal interim analyses. Any IAD may be skipped, and additional analysis may be added. If an unplanned IAD is deemed necessary, the Lilly clinical pharmacologist, investigator, or designee will consult with the appropriate medical director or designee to determine if it is necessary to amend the protocol.

The investigator and the Lilly clinical pharmacologist or sponsor team will determine dose escalation based upon their review of the safety data and PK data when available and/or required.

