7. TREATMENTS

The following is a list of the study treatment names that will be used in the TFLs.

For each part, the data from PBO groups will be pooled across cohorts as 1 PBO group.

Part A:

Cohort	Study Treatment Name	Treatment order in TFL	
A 11	Placebo IV	1	
All	Placebo SC	2	
1	mg LY3872386 IV	3	
2	mg LY3872386 IV	4	
3	mg LY3872386 IV	5	
4	mg LY3872386 IV	6	
5	mg LY3872386 SC	7	
6	mg LY3872386 IV	8	
7	mg LY3872386 SC	9	
8	mg LY3872386 IV	10	

Abbreviations: IV = intravenous; SC = subcutaneous

Part B:

Cohort	Study Treatment Name	Treatment order in TFL
All	Placebo	1
1	mg LY3872386 TBD (IV or SC) TBD (CCI or CCI)	2
2	mg LY3872386 TBD (IV or SC) TBD (CCI or CCI)	3
Abbreviations	IV = intravenous: CC	SC = subcutaneous

Part C:

Group	Study Treatment Name	Treatment order in TFL	
1	mg prednisone PO QD	1	
2	mg prednisone PO QD	2	
3	mg prednisone PO QD	3	

Abbreviations: PO = oral administration; QD = once daily

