10.3 Pharmacokinetic Assessment

10.3.1 Pharmacokinetic Analysis

The following PK parameters will be determined using noncompartmental methods in validated software program Phoenix WinNonlin (Certara, Version 8.3.5 or higher):

Plasma concentrations of LY3872386, total antibody, LY3558533 (free payload) will be used to determine the following PK parameters for Parts A and part B, where possible:

CONFIDENTIAL Protocol Reference: J4L-MC-KMAA

For Part A - SAD (Cohorts 1 to 8):

Parameter	Units ^a	Definition
AUC(CCI)	μg.h/mL	area under the concentration versus time curve from time 0 to hours post dose.
AUC(CCI)	μg.h/mL	area under the concentration versus time curve from time 0 to hours post dose.
AUC _(0-t)	μg.h/mL	area under the concentration versus time curve from time 0 to the time of the last quantifiable concentration.
$\mathrm{AUC}_{(0-\infty)}$	μg.h/mL	area under the concentration versus time curve from time 0 to infinity
$\%AUC_{(tlast-\infty)}$	%	fraction of AUC(0-∞) extrapolated
C_{max}	$\mu g/mL$	maximum observed drug concentration
t_{max}	h	time of the maximum observed drug concentration
t _{1/2}	h	half-life associated with the terminal rate constant (λ_z) in non-compartmental analysis
CL/F	L/h	apparent total body clearance of drug calculated after extra-vascular administration (for LY3872386 only)
V _z /F	L	apparent total body clearance of drug calculated after extra-vascular administration (for LY3872386 only)
CL	L/h	total body clearance of drug calculated after intravenous administration (for LY3872386 only)
Vz	L	Volume of distribution during terminal phase (LY3872386 IV dosing)
F	%	bioavailability of drug. Fraction of extravascular dose reaching the general circulation compared to an IV administration

^a Units are based on concentration units (provided by the bioanalytical lab or preferred units for presentation of PK parameters) and dose units used in the study.

For Part B - MAD (Cohorts 1 and 2), Profile Day 1 and Day 85:

Parameter	Unitsa	Definition
AUC _(0-t)	μg.h/mL	area under the concentration versus time curve from time 0 to the time of the last quantifiable concentration. b
AUC_{τ}	μg.h/mL	area under the concentration versus time curve during one dosing interval
$\mathrm{AUC}_{(0-\infty)}$	μg.h/mL	area under the concentration versus time curve from time 0 to infinity ^b
$\%AUC_{(tlast-\infty)}$	%	fraction of AUC(0- ∞) extrapolated
C_{max}	$\mu g/mL$	maximum observed drug concentration

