t_{max}	h	time of the maximum observed drug concentration
$t_{1/2}$	h	half-life associated with the terminal rate constant (λ_z) in non-compartmental analysis
CL/F	L/h	apparent total body clearance of drug calculated after extra-vascular administration (for LY3872386 only)
V _z /F	L	apparent total body clearance of drug calculated after extra-vascular administration (for LY3872386 only)
CL _{ss} /F	L/h	apparent total body clearance of drug calculated after extra-vascular administration (for LY3872386 only)
V _{ss} /F	L	apparent volume of distribution at steady state after extra-vascular administration (for LY3872386 only)
CL	L/h	total body clearance of drug calculated after intravenous administration (for LY3872386 only)
V_z	L	volume of distribution during the terminal phase after intravenous administration (for LY3872386 only)
$\mathrm{CL}_{\mathrm{ss}}$	L/h	total body clearance of drug at steady state calculated after intravenous administration (for LY3872386 only)
$ m V_{ss}$	L	volume of distribution at steady state following intravenous administration (for LY3872386 only)
RA _{AUC}		accumulation ratio calculated for steady state AUC τ versus Day 1
RA_{cmax}		accumulation ratio calculated for steady state Cmax versus Day 1

^a Units are based on concentration units (provided by the bioanalytical lab or preferred units for presentation of PK parameters) and dose units used in the study.

CONFIDENTIAL

Protocol Reference: J4L-MC-KMAA

^b The AUC will be calculated using the linear trapezoidal rule for increasing concentrations and the logarithmic rule for decreasing concentrations (linear up/log down rule).

CL/F, Vz/F, CL, Vz will be reported for profile day 1, whereas CLss/F, Vss/F, CLss, Vss will be reported for profile day 85.

CONFIDENTIAL Protocol Reference: J4L-MC-KMAA

Plasma concentrations of prednisone and prednisolone will be used to determine the following PK parameters for Part C, where possible:

For Part C (Day 1, Day 7, and Day 30):

Parameter	Unitsa	Definition
AUC _τ	μg.h/mL	area under the concentration versus time curve during one dosing interval
$\mathrm{AUC}_{(0\text{-t})}$	μg.h/mL	area under the concentration versus time curve from time 0 to the time of the last quantifiable concentration.
$\mathrm{AUC}_{(0\text{-}\infty)}$	μg.h/mL	area under the concentration versus time curve from time 0 to infinity
$\%AUC_{(tlast-\infty)}$	%	fraction of AUC(0-∞) extrapolated
C_{max}	$\mu g/mL$	maximum observed drug concentration

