t_{max}	h	time of the maximum observed drug concentration
$t_{1/2}$	h	half-life associated with the terminal rate constant (λ_z) in non-compartmental analysis
CL/F	L/h	apparent total body clearance of drug calculated after extra-vascular administration (for prednisone only)
V_z/F	L	apparent total body clearance of drug calculated after extra-vascular administration (for prednisone only)
CL _{ss} /F	L/h	apparent total body clearance of drug calculated after extra-vascular administration (for prednisone only)
V _{ss} /F	L	apparent volume of distribution at steady state after extra-vascular administration (for prednisone only)

^a Units are based on concentration units (provided by the bioanalytical lab or preferred units for presentation of PK parameters) and dose units used in the study.

CL/F and Vz/F will be reported for profile day 1, whereas CLss/F and Vss/F will be reported for profile day 30.

If deemed necessary, additional model-based analysis may be performed.

Additional PK parameters may be calculated, as appropriate. The software and version used for the final analyses will be specified in the clinical study report. Any exceptions or special handling of data will be clearly documented within the final study report.

Formatting of tables, figures and abbreviations will follow the Eli Lilly Global PK/PD/TS Tool: NON-COMPARTMENTAL PHARMACOKINETIC STYLE GUIDE. The version of the tool effective at the time of PK analysis will be followed.

General PK Parameter Rules

• Actual sampling times will be used in the final analyses of individual plasma PK parameters, except for pre-dose sampling times which will be set to zero.

Alysis Plan CONFIDENTIAL 8524153 Protocol Reference: J4L-MC-KMAA

- C_{max} and t_{max} will be reported from observed values. If C_{max} occurs at more than one time point, t_{max} will be assigned to the first occurrence of C_{max} .
- AUC parameters will be calculated using a combination of the linear and logarithmic trapezoidal methods (linear-log trapezoidal rule). The linear trapezoidal method will be applied up to t_{max} and then the logarithmic trapezoidal method will be used after t_{max}. The minimum requirement for the calculation of AUC will be the inclusion of at least three consecutive plasma concentrations above the lower limit of quantification, with at least one of these concentrations following C_{max}.

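### If a Part B cohort is dosed SC and no PK sample is added or moved, RA_Cmax compares unmatched Day 85 and Day 1 profiles and would usually overstate accumulation

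*SAP*

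**What the plan says.** SAP 10.3.1 (Part B table, profile days 1 and 85) lists RA_Cmax as the "accumulation ratio calculated for steady state Cmax versus Day 1", with RA_AUC beside it. The general PK rules in the same section say that Cmax and tmax "will be reported from observed values". No rule limits either ratio by route or requires the two profiles to share sampling times.

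SAP 7 leaves the Part B treatment as "mg LY3872386 TBD (IV or SC) TBD", so an SC cohort is possible.

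In both Part B schedules (Protocol 1.3.2.1 and 1.3.2.2) the PK row reads "P, EOI, 1 hr, and 3 hr" at Visit 2 (Day 1) and at Visit 8. After Visit 2 the next PK sample is at Visit 3. After Visit 8 it is at Visit 801.

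Three protocol provisions allow changes to sampling. Section 8 (introduction) says "Modifications may be made to the time points based on emerging clinical information". Section 8.4 says "a maximum of 3 additional blood samples may be collected as additional unscheduled time points during the study", if warranted and agreed. Section 9.4.1 says of the interim reviews: "A review of these data will help guide implementation of this study (such as adjustment to blood sampling time". SAP 10.3.1 also allows further model-based analysis if it is judged necessary.

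**The concern.** A ratio of two observed maxima measures accumulation only if both maxima are found equally well. After IV dosing the peak lies near the end of the infusion, which is sampled on both days, so RA_Cmax for the ADC and total antibody is sound. After SC dosing an antibody-like molecule may be expected to peak days later. Day 1 has no sample between 3 h and about Day 15; Day 85 has one near 72 h. The denominator then misses its peak and the numerator nearly catches it.

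The SAP would print a ratio that partly reflects the visit schedule, and modest accumulation could be read as marked. Repeat-dose Cmax and AUC are secondary endpoints and the study is meant to inform later trials, so the ratio is likely to be read. It is not itself a named endpoint, and no visible decision rule uses it.

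**Working it through.** **1. Sample counts.** The visible PK rows, without the early-discontinuation visit, were checked against the blood-volume tables in Protocol 10.2.1.
- First schedule: 4 (V2) + 5 × 2 (V3-V7) + 4 (V8) + 4 (V801-V804) = 22. Stated: 22.
- Second schedule: 4 + 1 + 2 + 1 + 2 + 1 + 4 (V2-V8) + 5 (V801-V805) = 20. Stated: 20.

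Both agree, so redaction hides no extra scheduled PK sample.

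**2. Visit days.** These are blacked out in the schedules and are inferred from the amendment tables. HbA1c days give V8 = Day 85 ± 1 d. Ocular-pressure days give V4, V6 and V801 = Days 29, 57 and 88, each ± 1 d. Amendment a gives V3 = Day 15 in the second schedule; seven evenly spaced doses from Day 1 to Day 85 give the same day in the first. Intervals of 14 and 28 d agree with the 336 h and 672 h AUCs defined under Table KMAA.4.

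V801 is therefore nominally 72 h after the Day 85 dose. If only V801 moves, the range is 48-96 h. If both windows apply, it is 24 h (Day 86 to Day 87) to 120 h (Day 84 to Day 89).

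**3. Model (assumed).** One compartment with first-order SC absorption, dose scaled to 1: C(t) = ka/(ka − ke) × (e^(−ke·t) − e^(−ka·t)), summed over doses; ke = ln 2 / half-life; ka solves ln(ka/ke)/(ka − ke) = Tmax. V3 is counted in the Day 1 profile, which is the generous choice.

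**4. Worked example.** Half-life 14 d and Tmax 3 d give ke = 0.0495/d, ka = 1.076/d and ka/(ka − ke) = 1.048.
- Day 1: true peak C(3 d) = 0.862; C(3 h) = 0.125; C(14 d) = 1.048 × 0.5 = 0.524. The observed Cmax is 0.524, or 61% of the peak.
- Day 85, sample at 72 h: 1.048 × (0.862 × S − 0.040), where S sums the earlier doses. Every 14 d (7 doses) S = 1.984, giving 1.75; every 28 d (4 doses) S = 1.328, giving 1.16. The true peaks are 1.77 and 1.16.

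| Interval | RA_Cmax as sampled | True RA_Cmax | Ratio of the two |
|---|---|---|---|
| 14 d | 1.75/0.524 = 3.34 | 1.77/0.862 = 2.05 | 1.63 |
| 28 d | 1.16/0.524 = 2.21 | 1.16/0.862 = 1.35 | 1.64 |

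**5. Grid.** Half-life 7/14/21 d; Tmax 2/3/5/7 d; V802 14 or 28 d after the last dose; both intervals: 3 × 4 × 2 × 2 = 48 runs per V801 time.

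| V801 | Runs | RA_Cmax / true | Median | Below 1 |
|---|---|---|---|---|
| 72 h | 48 | 1.1-2.9 | 1.4 | 0 |
| 48, 72, 96 h | 144 | 0.94-3.1 | 1.4 | 6 |
| 24 h | 48 | 0.67-2.8 | 1.28 | 12 |

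Day 1 captures 33-86% of its true peak. Day 85 captures 84-100% at 72 h, as little as 70% at 48 h and 50% at 24 h. The 6 reversals at 48 h are all 4-weekly with Tmax 7 d.

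**6. Wider check.** With half-life 3-28 d, Tmax 2-10 d, V801 at 72 h and no later sample in the Day 85 interval, 91 of 98 runs overstate. The 7 exceptions (0.86-0.998) are all 4-weekly with Tmax of 8 d or more. With assumed saturable elimination 23 of 24 runs overstate (1.16 to 10 times true); the exception is 0.84.

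**7. RA_AUC.** With 2-weekly dosing the Day 1 maximum is the last sample, so the SAP's requirement for a concentration after Cmax blocks AUC. With 4-weekly dosing AUC is allowed if the 3 h sample is quantifiable, and RA_AUC is then 1.1-1.8 times true at 72 h.

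**The case against.** The strongest reply is that the sponsor can adapt. Part B dose and route are to be confirmed from Part A data, the first interim data review includes SC Cohort 5, and adjusting sampling times is a named use of these reviews. Up to three unscheduled samples and a model-based analysis are also available. All of this stands and lowers the severity. But each provision is optional, none is tied to this ratio, and the SAP as written would still print it.

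Second, the size rests on chosen parameters, since no human SC half-life or Tmax is visible. That stands. The body of Protocol 8.4.1 and the schedule comments are also not visible. The count in step 1 excludes extra samples, but not different times for SC cohorts.

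Third, the tmax listing would hint at the artefact: about 14 d on Day 1 against about 3 d on Day 85. True, but a hint does not correct the ratio.

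A reader might also infer that the SAP promises Day 1 SC CL/F and Vz/F that it cannot deliver. The documents do not support that as an error: the table is introduced with "will be used to determine the following PK parameters for Parts A and part B, where possible", so parameters that cannot be estimated are simply left out.

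**Conclusion.** The point holds, as a minor one. If SC is chosen and sampling stays as scheduled, RA_Cmax for the ADC and total antibody would usually overstate accumulation. In the assumed model the ratio is 1.1-2.9 times true at the nominal 72 h and 0.94-3.1 times true over 48-96 h, median about 1.4. The sampling mismatch is read from the schedules and inferred visit days; the direction and size are model results.

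Three stronger readings are tempting and not supported. The ratio is not always inflated: it reverses in some 4-weekly runs with an early V801 or slow absorption. No factor can be quoted as the bias of this trial. And the Part B PK endpoints are not shown to be unsound in general: IV RA_Cmax for these two analytes is unaffected, and in the model SC Day 85 Cmax is close to the true peak when V801 falls near 72 h. Free payload was not assessed.

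**What to change.** In the SAP Part B parameter table, for SC cohorts only:

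1. Do not report noncompartmental RA_Cmax or RA_AUC when the Day 1 and Day 85 profiles have unmatched sampling times.
2. Mark Day 1 Cmax and tmax as limited by sampling.
3. Describe accumulation by the ratio of predose concentrations already drawn, where quantifiable: Day 85 over Day 15 for 2-weekly dosing, Day 85 over Day 29 for 4-weekly. State that it approximates AUC accumulation, may be somewhat low or high, and covers one dose fewer. Alternatively, use the model-based analysis that SAP 10.3.1 already allows.

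Put no fixed percentage in the SAP. In the assumed runs the predose ratio is 80-98% (2-weekly) or 90-99% (4-weekly) of true RA_AUC under linear kinetics, but 81-110% under saturable elimination.

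The cost is SAP wording and no new visit. The drawbacks are that the predose ratio is undefined if a trough is below quantification, and that it describes dose 6 (2-weekly) or dose 3 (4-weekly).

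If SC is chosen and a sample near 72 h after dose 1 is added under Protocol 8, 8.4 or 9.4.1, RA_Cmax can be kept. In the assumed model it is then 0.98-1.26 times true with both samples at 72 h, or 0.88-1.30 if only Visit 801 drifts within 48-96 h. That costs one extra visit. IV cohorts: no change.

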- Individual concentrations will be plotted utilizing actual sampling times.
- The terminal point selections will be indicated on a semi-logarithmic plot.

Average Concentration vs. Time Profiles

- The average concentration profiles will be graphed using scheduled (nominal) sampling times.
- The average concentration profiles will be graphed using arithmetic average concentrations.
- The pre-dose average concentration for single-dose data will be set to zero. Otherwise, only quantifiable concentrations will be used to calculate average concentrations.
- Concentrations at a sampling time exceeding the sampling time window specified in the protocol, or $\pm 10\%$, will be excluded from the average concentration profiles.
- Concentrations excluded from the mean calculation will be documented in the final study report.
- A concentration average will be plotted for a given sampling time only if 2/3 of the individual data at the time point have quantifiable measurements that are within the sampling time window specified in the protocol or ± 10%. An average concentration estimated with less than 2/3 but more than 3 data points may be displayed on the mean concentration plot if determined to be appropriate and will be documented within the final study report.

Treatment of Outliers during Pharmacokinetic Analysis

Application of this procedure to all PK analyses is not a requirement. Rather, this procedure provides justification for exclusion of data when scientifically appropriate. This procedure describes the methodology for identifying an individual value as an outlier for potential exclusion but does not require that the value be excluded from analysis. The following methodology will not be used to exclude complete profiles from analysis.

CONFIDENTIAL Protocol Reference: J4L-MC-KMAA

Data within an Individual Profile

A value within an individual profile may be excluded from analysis if any of the following criteria are met:

- For PK profiles during single dosing of non-endogenous compounds, the concentration in a pre-dose sample is quantifiable.
- For PK profiles during multiple dosing, the concentration of the pre-dose sample exceeds all measured concentrations for that individual in the subsequent post-dose samples.
- For any questionable datum that does not satisfy the above criteria, the profile will be evaluated, and results reported with and without the suspected datum.

Data between Individual Profiles

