- 1. If n<6, then the dataset is too small to conduct a reliable range test. Data will be analyzed with and without the atypical value, and both sets of results will be reported.
- 2. If n≥6, then an objective outlier test will be used to compare the atypical value to other values included in that calculation:
 - a. Transform all values in the calculation to the logarithmic domain.
 - b. Find the most extreme value from the arithmetic mean of the log transformed values and exclude that value from the dataset.
 - c. Calculate the lower and upper bounds of the range defined by the arithmetic mean $\pm 3*SD$ of the remaining log-transformed values.
 - d. If the extreme value is within the range of arithmetic mean $\pm 3*SD$, then it is not an outlier and will be retained in the dataset.
 - e. If the extreme value is outside the range of arithmetic mean $\pm 3*SD$, then it is an outlier and will be excluded from analysis.

If the remaining dataset contains another atypical datum suspected to be an outlier and $n \ge 6$ following the exclusion, then repeat step 2 above. This evaluation may be repeated as many times as necessary, excluding only one suspected outlier in each iteration, until all data remaining in the dataset fall within the range of arithmetic mean $\pm 3*SD$ of the log-transformed values.

Reporting of Excluded Values

Individual values excluded as outliers will be documented in the final report. Approval of the final report will connote approval of the exclusion.

CONFIDENTIAL Protocol Reference: J4L-MC-KMAA

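### The SAP says both that a flagged PK outlier need not be excluded and that it will be, and for n≥6 it does not require results with and without the value

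*SAP*

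**What the plan says.** All the text is in SAP Section 10.3.1, under the treatment of outliers.

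- **Opening paragraph.** The procedure is optional: "Application of this procedure to all PK analyses is not a requirement". It identifies candidates for exclusion but "does not require that the value be excluded from analysis". It also has a limit: "The following methodology will not be used to exclude complete profiles from analysis".
- **Between profiles, n<6.** The rule is "then the dataset is too small to conduct a reliable range test". It continues: "Data will be analyzed with and without the atypical value, and both sets of results will be reported".
- **Between profiles, n≥6.** Here "an objective outlier test will be used to compare the atypical value to other values included in that calculation". The values are log-transformed and the one furthest from the mean is set aside. It is then compared with the mean ± 3 SD of the rest. If it falls outside, "then it is an outlier and will be excluded from analysis" (step 2e). The test may be repeated while n is at least 6.
- **Reporting.** "Individual values excluded as outliers will be documented in the final report". Approval of the final report counts as approval of the exclusion.

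Within a single participant's profile, a questionable value that meets none of the listed criteria is reported both ways. No such duplicate result is required in the between-profile branch for n≥6.

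**The concern.** Two analysts could follow the same text with the same flagged value and report different results. One would keep it under the opening paragraph and the other would remove it under step 2e. Nothing says which text prevails.

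The n≥6 branch also has the weakest safeguard. The SAP treats n<6 as too few for a dependable test and asks for both results. From n=6 it relies on the test and asks only that the exclusion be documented. That is sound only if the test becomes dependable at about n=6.

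If step 2e is followed on a genuine value, the only required summary understates variability. Cmax and AUC are the secondary endpoints (SAP Section 4) and are summarised by geometric mean and geometric CV (SAP Section 10.1). The SAP does not say whether the test is applied to such parameters or to concentrations at a time point, so both readings are worked below.

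**Working it through.** **Inputs.** From the SAP: the largest deviation is tested, the mean and SD come from the other n−1 log values, the multiplier is 3 at every n, and AUC and Cmax are treated as log-normal (Section 10.1). Assumed: n, because cohort sizes are redacted, and true CVs of 15%, 30% and 50%, because none is given. The log SD is `sqrt(ln(1+CV²))`; for CV 30% this is sqrt(ln 1.09) = 0.294. The plan states no error rate for the test, so there is no figure of its own to reproduce.

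**Flag rate on clean data.** For any one value, the deviation from the mean of the others, divided by `SD·sqrt(1+1/(n−1))`, follows t with n−2 degrees of freedom. Summing over n values gives

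`P(flag) ≈ n · P(|t(n−2)| > 3/sqrt(1+1/(n−1)))`

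At n=6 the threshold is 3/sqrt(1.2) = 2.739 on 4 df. The two-sided probability is 0.0520, and 6 × 0.0520 = 0.312. Simulation of steps 2a–2e, run once on each of 400,000 data sets per n, agrees:

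| n | formula | simulated |
|---|---|---|
| 5 | 0.374 | 0.374 |
| 6 | 0.312 | 0.312 |
| 8 | 0.247 | 0.247 |
| 10 | 0.216 | 0.215 |
| 12 | 0.199 | 0.198 |

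The rate does not depend on the CV. It is high because the SD comes from few values and the most extreme of n is the one tested. With repetition, two or more clean values go in 6.8% of data sets at n=8 and 4.1% at n=12; at n=6 only one can go.

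**Effect if the test is applied to Cmax or AUC.** The geometric CV is `sqrt(exp(s²)−1)`, where s is the SD of the log values. Means over the flagged clean data sets, before and after dropping the value:

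| True CV | n=6: CV | n=6: shift in geometric mean | n=12: CV | n=12: shift in geometric mean |
|---|---|---|---|---|
| 15% | 14.3% → 7.6% | 5.1% | 14.7% → 10.4% | 3.1% |
| 30% | 28.7% → 15.0% | 10.0% | 29.4% → 20.6% | 6.1% |
| 50% | 48.2% → 24.5% | 16.1% | 49.1% → 33.8% | 9.8% |

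The relative fall in CV is about 47–49% at n=6 and 29–31% at n=12.

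**Averaged over all data sets,** if the test were always run and followed once, the mean CV falls far less. At n=6 it goes from 14.3% to 12.2%, 28.7% to 24.4% and 48.2% to 40.8%. At n=12 it goes from 14.7% to 13.8%, 29.4% to 27.7% and 49.1% to 46.1%.

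**Effect if applied to time-point concentrations.** One exclusion moves that point's arithmetic mean by 5.1%, 10.0% and 16.1% (n=6) or 3.1%, 6.3% and 10.6% (n=12) at the three CVs. Cmax and AUC summaries are not directly affected.

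**Dose proportionality (SAP Section 10.3.2).** This used the six Part A IV cohorts (1, 2, 3, 4, 6 and 8), assumed 3-fold dose steps, n=6 or 12 per cohort, and trials with exactly one flagged value. Dropping it multiplies the half-width of the slope's 90% CI by 0.973–0.976. Coverage goes from 0.896–0.906 to 0.870–0.879.

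**The case against.** The strongest reply is that the opening paragraph governs everything below it. It also says that the procedure serves to justify dropping data where that is scientifically warranted. On that reading step 2e is the last line of an optional procedure, and the 3-SD result alone removes nothing. This is a reasonable reading, but the SAP does not state it, step 2e is unconditional, and no second result is required for n≥6 either way.

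It can also be said that the documents set no false-flag target, so calling the test poorly calibrated applies an outside standard, and that the rates describe running it on every clean data set. The second part stands: the test is optional and starts from a value already thought unusual, so the realised rate is unknown. The comparison that matters uses the SAP's own boundary: 37% at n=5, where the SAP distrusts the test, against 31% at n=6, where it relies on it.

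Transparency is partly provided. Excluded values are documented and data are listed, so a reader could recompute. That limits the harm, but it does not show the effect on the reported summary.

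Finally, dual reporting could grow. Part A alone has eight cohorts, three analytes and a 13-row parameter table. The burden depends on how often values are flagged, and if that is often, the second result matters more.

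**Conclusion.** The concern holds. The two texts disagree on whether a flagged value is removed, and the n≥6 branch lacks the with-and-without result that the SAP requires for n<6, although the test is scarcely more dependable at n=6 than at n=5. Where a genuine Cmax or AUC value is flagged and dropped, the mean geometric CV falls by roughly 30–50% over n=6 to 12.

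These sizes rest on log-normal data, assumed n and CV, and the test being run and followed. If cohorts yield fewer than six values, the existing n<6 rule already covers them. The outputs are secondary and descriptive, no hypothesis is tested, and the effect on the dose-proportionality interval is small. This should be corrected as a reporting weakness; it does not undermine the trial's conclusions.

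**What to change.** 1. Reword step 2e so that a value outside the range is flagged as a potential outlier, in line with the opening paragraph.
2. For n≥6, apply the SAP's own n<6 rule: report results with and without any flagged value.
3. As a clarification, state whether the test applies to PK parameters, to time-point concentrations or to both.

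The 3-SD cut-off can stay as a screen, so no detection of true errors is lost. The cost is a few lines of SAP text and an extra summary row whenever a value is flagged. Reported CVs may be slightly larger, and readers will see two results where one is now required.

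An n-dependent cut-off is optional and involves a trade-off. Holding false flags at an illustrative 5% needs `t(1−0.05/(2n), n−2)·sqrt(1+1/(n−1))`, which is 5.31 SD at n=6 and 3.86 SD at n=12. At CV 30%, detection of a single 3-fold error then drops from 73.5% to 28.8% (n=6) or from 74.6% to 49.9% (n=12). Reporting both results avoids that loss.
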